### **Objectives:**

The **primary objectives** of this study are:

- To assess the efficacy of new direct acting oral antivirals: LDV/SOF FDC (Harvoni®) or SOF/VEL FDC (Epclusa®) in patients with chronic HCV infection and MC, measuring the proportion of subjects who attain SVR at 4 and 24 weeks after cessation of treatment.
- To assess efficacy of new direct acting oral antivirals: LDV/SOF FDC (Harvoni®) or SOF/VEL FDC (Epclusa®) in patients with mixed cryoglobulinemia (MC) secondary to chronic HCV infection:

- A complete response is defined as disappearance of arthropathy or kidney involvement, and/or purpura, and >50% reduction in IgM-RF and cryocrit.
- A partial response is a 10-50% reduction in cryocrit and one (but not all) clinical and laboratory signs of systemic vasculitis.

The **secondary objectives** of this study are:

- To assess immunological response of MC to new direct acting oral antivirals: LDV/SOF (Harvoni®) or SOF/VEL FDC (Epclusa®) treatment measuring:
  - FACS/CyTOF analysis of PBMC to determine the effect of DAA treatment on cell-surface markers or MC
  - analysis of isolated mixed cryoglobulins for localization of viral RNA, the presence of HCV core antigen, C1q protein, C1q binding activity and soluble gC1qR.
  - accumulate kinetic data to address the issues of (a) redistribution of viral RNA and core protein between cryoprecipitable and noncryoprecipitable immune complexes with treatment (27) (b) persistence of cryoglobulins and cryoglobulinemic vasculitis following apparent clearance of virus (13,14,28); and (c) persistence of virus in PBMC or cryoprecipitates following apparent systemic clearance (i.e. occult infection) (29).
- To assess safety and tolerability of new direct acting oral antivirals: LDV/SOF FDC (Harvoni®) or SOF/VEL FDC (Epclusa®) in patients with chronic HCV infection and MC.

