#### **Evaluation Criteria:**

- Efficacy:
  - Efficacy of treatment on MC will be assessed as follows:
    - Complete response is defined as disappearance of arthropathy or kidney involvement, and/or purpura, and >50% reduction in IgM-RF and cryocrit.
    - Partial response is a 10-50% reduction in cryocrit and one (but not all) clinical and laboratory signs of systemic vasculitis.

- Efficacy of treatment on HCV infection will be evaluated using scheduled assessments of HCV RNA performed using COBAS® TaqMan® HCV Test, v2.0 for use with Ampliprep.
- Safety: AEs and laboratory tests will be collected throughout the study.

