We have a long-standing interest in the cryopathies, including early recognition of the prevalence of hepatic disease among patients affected by purpura, arthralgias and MPGN, progression to liver failure in some patients with long-term follow-up (15), characterization of the clonality of the IgMk component of type 2 cryoglobulins, phlogistic activity of mixed cryoglobulins with regard to complement and other mediators

(16), and methodology for the accurate isolation of characterization of cold-precipitable RFs (17). Our current data base includes 180 patients with the syndrome of MC with long-term follow-up of 40 patients spanning 1960-2010. The cohort of MC since the description of HCV in 1989 is 55% female, with an overall incidence of 68% cutaneous disease, 56% arthropathy, 35% nephropathy, 58% neuropathy, 60% type 2/40% type 3 mixed cryoglobulins, and 60% HCV. In addition, we recently completed a retrospective chart review of 51 HCV-positive patients with MC seen at our medical center between 2003-2013, 60% having genotype 1, 14% genotype 2 and 10% genotype 3, in which we specifically analyzed the efficacy of current antiviral therapy and Rituximab in this cohort with regard to progression of liver disease to transplantation and MPGN to end-stage renal disease requiring dialysis (16). This experience may be compared to a very recent report from Italy which noted a ~30% incidence of genotype 2 among their MC patients receiving direct acting antivirals (DAA) treatment (19).

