## 2. OBJECTIVES

The **primary objectives** of this study are:

- To assess the efficacy of new direct acting oral antivirals: LDV/SOF FDC (Harvoni®) or SOF/VEL FDC (Epclusa®) in patients with chronic HCV infection and MC, measuring the proportion of subjects who attain SVR at 4 and 24 weeks after cessation of treatment.
- To assess efficacy of new direct acting oral antivirals: LDV/SOF FDC (Harvoni®) or SOF/VEL FDC (Epclusa®) in patients with MC secondary to chronic HCV infection:
  - A **complete response** is defined as disappearance of arthropathy or kidney involvement, and/or purpura, and >50% reduction in IgM-RF and cryocrit.
  - A **partial response** is a 10-50% reduction in cryocrit and one (but not all) clinical and laboratory signs of systemic vasculitis (see below) (33)

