***Immunologic Responses:***

- Kinetics of response with regard to *compartmentalization of viral RNA and core antigen* between cryoprecipitable and non-cryoprecipitable immune complexes.
- Serial *quantitation of cryoprecipitates* and correlation with RF titers determined by nephelometry, and C4 levels measured in freshly collected serum.
- *C1q and C1q binding assays* are available through our clinical immunology laboratory, and will be compared to our previously published experience in MC with these assays. Quantitation of soluble forms of the *receptor for the globular domain of C1q (gC1qR)* is available through the laboratory of [name] (State University of New York, Stony Brook) (32).
- *Regression of clonality* assessed by immunofixation of isolated cryoprecipitates, and kappa/lambda Free Light Chain (FLC) measurements in blood.
- *Regression of clonality and lymphoproliferation* assessed by FACS analysis for specific B-cell subsets and MC cross-reactive idiotypes.
- Isolation *PMBCs for analyzing by FACS/ Cytometry* cell-surface markers during and after DAA treatment

Results will be compared to previous published studies, as well as unpublished experience, that have delineated the natural history of type 2 cryoglobulinemia, and the response to immunomodulatory therapies, including IFN, Ribavirin and Rituximab (27, 38).

The **secondary objectives** of this study are:

- To assess immunological response of MC to new direct acting oral antivirals: SOF/VEL FDC (Harvoni®) or SOF/VEL FDC (Epclusa®) treatment measuring:
  - FACS/CyTOF analysis of PBMC
  - analysis of isolated mixed cryoglobulins for localization of viral RNA, the presence HCV core antigen, C1q protein, C1q binding activity and soluble gC1qR.
  - accumulate kinetic data to address the issues of:
    - (a) redistribution of viral RNA and core protein between cryoprecipitable and noncryoprecipitable immune complexes with treatment (27);
    - (b) persistence of cryoglobulins and cryoglobulinemic vasculitis following apparent clearance of virus (13,28 ,29); and
    - (c) persistence of virus in PBMC or cryoprecipitates following apparent systemic clearance (i.e. occult infection) (29).
- To assess safety and tolerability of new direct acting oral antivirals: LDV/SOF FDC (Harvoni®) LDV/SOF FDC (Harvoni®) or SOF/VEL FDC (Epclusa®) in patients with chronic HCV infection and MC.

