10. Null or partial response to previous therapies for MC, including corticosteroids, cytotoxic agents (cyclophosphamide, azathioprine), hydroxychloroquine, methotrexate, mono- or combination therapy with IFN $\alpha$ /PEG-IFN and ribavirin, and/or CD20 depletion with Rituximab.
- a. Patients can be on ongoing treatment with one of the drugs described above at inclusion unless there is significant DDI.
11. Subjects has the following laboratory parameters at screening:
- a) ALT <10 x the upper limit of normal (ULN)
  - b) AST <10 x ULN
  - c) Adequate bone marrow function as indicated hematologic parameters listed below and/or bone marrow cellularity >60-70% average for age.
    - a. WBC >1500 /uL
    - b. Platelets > 50,000/uL
  - d) Direct bilirubin >2 x ULN
  - e) INR >1.5 x ULN unless subject has known hemophilia or is stable on an anticoagulant regimen affecting INR
12. Females of childbearing potential (as defined in Appendix 3) must have a negative serum pregnancy test at Screening and a negative urine pregnancy test on Baseline/Day 1 prior to treatment.

13. Male subjects and female subjects of childbearing potential who engage in heterosexual intercourse must agree to use protocol specified method(s) of contraception as described in Appendix 3.
14. Lactating females must agree to discontinue nursing before the study drug is administered.
15. Subject must be of generally good health, with the exception of chronic HCV infection, as determined by the Investigator.
16. Subject must be able to comply with the dosing instructions for study drug administration and able to complete the study schedule of assessments.

**Note: Definition of Mixed Cryoglobulinemia** (patients must meet one of the five overlapping syndromes listed below and the presence/documentation of cold-precipitable immune complexes in blood on two different occasions.

- Clinical evidence of cryoglobulinemia, overlapping syndromes:
  1. Cutaneous vasculitis (Raynaud's phenomenon, purpura, skin ulcers, livedo, acrocyanosis)
  2. Glomerulonephritis (hypertension, hematuria, nephrotic syndrome)
  3. Arthropathy (arthralgias, arthritis)
  4. Neuropathy (peripheral and/or central nervous system, distal sensorimotor, mononeuritis multiplex)
  5. Sicca syndrome (xerostomia, xerophthalmia)

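### The cryoglobulinemia response rule is not ordered: partial response stops at a 50% cryocrit fall, so a larger fall can cost a patient the label

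*Combined protocol and SAP*

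**What the plan says.** Section 2 sets two primary objectives: virologic response, and response of MC itself. For MC, CR is "disappearance of arthropathy or kidney involvement, and/or purpura, and >50% reduction in IgM-RF and cryocrit", and PR is a "10-50% reduction in cryocrit and one (but not all) clinical and laboratory signs of systemic vasculitis". The Synopsis gives both definitions in the same terms under Objectives and under Evaluation Criteria, so the 50% ceiling on PR appears three times without variation.

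There is no third category, and no rule for a patient who meets neither definition. The only timing given with the primary objectives belongs to the virologic one: "measuring the proportion of subjects who attain SVR at 4 and 24 weeks after cessation of treatment". Section 6 schedules cryoglobulin analysis at on-treatment and post-treatment visits but designates none for judging MC response. Section 9 plans a frequency table and a 95% confidence interval for the SVR rate. It gives no analysis of CR or PR.

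**The concern.** On an ordered response scale, improving one component with the others held fixed should never lower the category. Here PR ends at the cryocrit fall where CR begins, but CR also demands an IgM-RF fall and clinical disappearance. A patient who passes 50% on cryocrit therefore leaves PR at once and enters CR only if those other requirements are met. Otherwise the better cryocrit result removes the label.

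This affects a primary objective in an open-label study. With the residual category, the reading of the clinical terms and the visit all unstated, each could be settled after the data have been seen. The planned comparison with published experience would inherit whatever choice was made.

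**Working it through.** The plan gives no figure for MC response, so the check is logical: apply the two definitions as written to a grid.

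**Inputs (Section 2)**
- CR: cryocrit fall >50%, IgM-RF fall >50%, and clinical disappearance. The conjunctions joining the manifestations allow two readings: all must clear (strict), or one suffices (lenient).
- PR: cryocrit fall from 10% to 50%, with some but not all signs meeting the sign criterion.

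**Assumptions.** PR does not say what a sign must do; I take clearance as meeting the criterion. The patient has at least two manifestations. In the table neither cryocrit nor RF counts as a sign. IgM-RF falls of 40% and 60% stand for 50% or less and more than 50%.

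| Signs cleared | IgM-RF fall | Label at 45% cryocrit fall | Label at 60%, strict CR | Label at 60%, lenient CR |
|---|---|---|---|---|
| None | 40% | none | none | none |
| None | 60% | none | none | none |
| Some | 40% | PR | none | none |
| Some | 60% | PR | none | CR |
| All | 40% | none | none | none |
| All | 60% | none | CR | CR |

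**Cryocrit axis.** Two of the six cells are PR at 45%. Above 50%, both lose the label under strict CR and one does under lenient CR. The cell with some signs cleared and IgM-RF down 40% loses it under both, because IgM-RF blocks CR however the clinical wording is read. An example is purpura cleared, arthropathy persisting and IgM-RF down 40%. Counting RF as a sign does not rescue this patient: one sign has cleared and one persists, so some but not all still holds.

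**Default of non-response.** Treating a patient who meets neither definition as a non-responder makes the set exhaustive, but the order stays reversed: a 45% fall is PR and a 60% fall is non-response.

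**Clinical axis.** Fix the cryocrit fall at 30%. With some signs cleared the patient is PR. With all cleared the patient fails PR (not all is required) and fails CR (cryocrit not above 50%), and so has no label.

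**Search for a repair elsewhere.** The cross-reference in Section 2 leads to the organ assessments under Clinical Responses, which add no CR or PR threshold, residual category or visit. Inclusion criterion 10 mentions null or partial response, but to earlier MC treatments. Section 9 concerns SVR.

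**Weight of one patient.** With n = 10, one relabelled patient moves a rate by 1/10 = 10 percentage points. As an illustration only, 5/10 = 50% has an exact (Clopper-Pearson) 95% interval of 18.7% to 81.3%, and 6/10 = 60% has 26.2% to 87.8%.

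**Check of a repaired rule.** Let PR be CR not met, cryocrit fall of at least 10% and at least one sign cleared, with all others non-response. At 45% the two cells with some cleared and the two with all cleared are PR (4 of 6), and the two with none cleared are non-response. At 60% every PR cell stays PR or becomes CR, under either reading of CR. No cell loses a label.

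**The case against.** The strongest reply is proportion. This is a 10-patient exploratory pilot with no hypothesis test or decision rule tied to MC response, and counting unlabelled patients as non-responders would be conservative. A 10-point shift is also small beside the exact intervals above. This stands as an argument about severity, but it does not restore the order of the categories.

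Second, the PR rule carries a literature citation, so its limits may be inherited, and changing them may cost comparability. The reference list describes that source as a validation of classification criteria, and the protocol does not say that the response limits come from it. The comparability cost is real and belongs with the fix.

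Third, serial kinetic data are intended, so having several assessment times is not itself a fault. That is fair: naming one visit for classification leaves the serial data intact.

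Four stronger readings are tempting, and the documents do not support them:
- A reader might infer that every fall above 50% loses the label. It does not. A patient who meets the other CR requirements moves properly to CR.
- A reader might use the site's own cohort ("68% cutaneous disease, 56% arthropathy, 35% nephropathy, 58% neuropathy") to estimate how many of the ten would be affected. Those rates describe organ involvement. Losing the label needs a cryocrit fall above 50% together with failure of another CR component, and no rate is given for that. Even a range for multi-organ disease depends on whether neuropathy counts: it qualifies for entry under Section 4.2 but is not named in CR.
- A reader might conclude that no visit is specified anywhere. Appendices 1a and 1b, the tables by visit, were not in the text reviewed, so the statement is limited to the rest of the protocol.
- A reader might say that the choice will be made after the data are seen. The text shows only that it could be.

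**Conclusion.** The concern holds. As written, a better cryocrit result can remove a response label that a worse one earns, and at a cryocrit fall of 50% or less the same can happen when all signs clear rather than some. The cryocrit reversal holds under either reading of the CR wording. It rests on the stated assumption that clearance of a sign satisfies the PR sign criterion. The number of trial patients affected cannot be derived from the documents.

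The missing residual category, the unnamed visit and the absence of an MC analysis in Section 9 add to the problem because they leave the classification open. In an exploratory pilot of this size this should be corrected before the data are analysed, but it does not invalidate the study. The ambiguous conjunctions in CR and the undefined change in a sign are gaps in detail, not further demonstrated errors.

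**What to change.** In Section 2 and in both Synopsis places:
- Define PR as CR not met, a cryocrit fall of at least 10% with no upper limit, and at least one sign other than cryocrit improved, with improvement defined by the investigators.
- Define non-response as all other patients.
- Have the investigators reconcile the CR conjunctions with the some-but-not-all condition in PR, and say whether RF counts as a sign.
- Judge all categories at one named visit that is already scheduled and chosen by the investigators. Post-treatment Week 24 is an example, since Section 6.3.2 places the Schirmer and saliva tests and the Neurology Department examination there. Keep the serial data as descriptive.

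In Section 9, add the CR rate and the CR-plus-PR rate, each with an exact 95% interval, and a patient-level listing of the components.

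The cost is wording and a check against Appendix 1b that cryocrit and IgM-RF are measured at Baseline and at the named visit. Serial quantitation of cryoprecipitates and "correlation with RF titers determined by nephelometry" are already planned in Section 2. The downside is that more patients can be labelled PR: on the grid, at a 45% cryocrit fall, 4 of 6 cells instead of 2 when RF is not a sign. Comparability with any published series that uses the capped definition may also fall. Listing the components, or also reporting the capped definition, limits that loss.

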### **Clinical Responses:**

- For patients whose predominant clinical manifestation is a *rheumatoid-like arthritis*, the primary evaluation will be a joint count in order to conform to American College of Rheumatology (ACR) outcome criteria (34).
- For patients whose predominant clinical manifestation is *vasculitis*, cutaneous disease will be assessed as number and distribution (scored as 1=<10; 2=>10; 3=upper and lower extremity; 4=complicated by ulcerations, gangrene or both) of purpuric lesions. Systemic vasculitis will be evaluated by a modification of the Birmingham Vasculitis Activity Score (35).
- *Glomerulonephritis* is defined as the presence of hematuria, proteinuria and red blood cell casts (i.e. an active urinary sediment) by urinalysis, further quantitated as total mg proteinuria, >300mg (upper limits of normal) on a 24 hour collection, or as the protein/creatinine ratio of a spot sample of urine. Concomitant renal insufficiency is defined as a serum creatinine >2.0mg/dL. Most patients will have also had renal biopsies showing typical features of membranoproliferative glomerulonephritis associated with cryoglobulinemia (36)

- *Neuropathy* is evaluated as being symmetrical or asymmetrical, pure sensory or sensorimotor, and further defined as number of extremities involved. Neuropathy may be corroborated by electrophysiologic testing as indicated (37).
- *Functional outcome* is evaluated as the Health Assessment Questionnaire (HAQ) .

***Virologic Responses:***

- Measure of *HCV antigens* in un-dissociated cryocomplexes relative to serum by sandwich ELISA for *core antigen* (31). The presence of HCV RNA in mixed cryoglobulins will be correlated with the presence of core antigen as a measure of un-encapsulated virus and nucleocapsid antigens.

***Immunologic Responses:***

- Kinetics of response with regard to *compartmentalization of viral RNA and core antigen* between cryoprecipitable and non-cryoprecipitable immune complexes.
- Serial *quantitation of cryoprecipitates* and correlation with RF titers determined by nephelometry, and C4 levels measured in freshly collected serum.
- *C1q and C1q binding assays* are available through our clinical immunology laboratory, and will be compared to our previously published experience in MC with these assays. Quantitation of soluble forms of the *receptor for the globular domain of C1q (gC1qR)* is available through the laboratory of [name] (State University of New York, Stony Brook) (32).
- *Regression of clonality* assessed by immunofixation of isolated cryoprecipitates, and kappa/lambda Free Light Chain (FLC) measurements in blood.
- *Regression of clonality and lymphoproliferation* assessed by FACS analysis for specific B-cell subsets and MC cross-reactive idiotypes.
- Isolation *PMBCs for analyzing by FACS/ Cytometry* cell-surface markers during and after DAA treatment

Results will be compared to previous published studies, as well as unpublished experience, that have delineated the natural history of type 2 cryoglobulinemia, and the response to immunomodulatory therapies, including IFN, Ribavirin and Rituximab (27, 38).

The **secondary objectives** of this study are:

- To assess immunological response of MC to new direct acting oral antivirals: SOF/VEL FDC (Harvoni®) or SOF/VEL FDC (Epclusa®) treatment measuring:
  - FACS/CyTOF analysis of PBMC
  - analysis of isolated mixed cryoglobulins for localization of viral RNA, the presence HCV core antigen, C1q protein, C1q binding activity and soluble gC1qR.
  - accumulate kinetic data to address the issues of:
    - (a) redistribution of viral RNA and core protein between cryoprecipitable and noncryoprecipitable immune complexes with treatment (27);
    - (b) persistence of cryoglobulins and cryoglobulinemic vasculitis following apparent clearance of virus (13,28 ,29); and
    - (c) persistence of virus in PBMC or cryoprecipitates following apparent systemic clearance (i.e. occult infection) (29).
- To assess safety and tolerability of new direct acting oral antivirals: LDV/SOF FDC (Harvoni®) LDV/SOF FDC (Harvoni®) or SOF/VEL FDC (Epclusa®) in patients with chronic HCV infection and MC.

### **3. STUDY DESIGN**

#### **3.1. Treatment plan and regimen**

This is a single-center, open-label study to evaluate the safety, tolerability and efficacy of new direct acting oral antivirals:

- Ledipasvir/Sofosbuvir 90mg/400 mg FDC (LDV/SOF;Harvoni®, for those subjects enrolled under protocol version 1 only) in patients with genotype 1 HCV infection and MC already enrolled in protocol version 1 or
- Sofosbuvir/Velpatasvir 400mg/100mg FDC (SOF/VEL; Epclusa®, for all subjects enrolled under protocol version 2) in patients with chronic genotypes 1-6 HCV infection and MC. All subjects enrolled in protocol version 2 will receive Epclusa® who have failed or only partially responded to other MC therapies.

Treatment duration is as follows:

Subjects that have been already enrolled and started treatment under protocol version 1 will continue and complete the planned treatment with LDV/SOF FDC (Harvoni®):

- Treatment naïve subjects will be treated for 12 weeks.
- Treatment experienced non-cirrhotic subjects will be treated for 12 weeks.
- Treatment experienced compensated cirrhotic subjects will be treated for 24 weeks.

Subjects enrolled under protocol version 2 will receive SOF/VEL FDC (Epclusa®):

- Treatment-naïve subjects will be treated for 12 weeks
- Treatment-experienced non-cirrhotic subjects will be treated for 12 weeks
- Treatment-experienced compensated cirrhotic subjects will be treated for 12 weeks

Approximately 20% of subjects may have cirrhosis.

